## 8.3.2 Adverse Event/Experience Severity Definitions

The severity of each adverse event or experience must be recorded as one of the following on the AE Log:

MildNo limitation of usual activitiesModerateSome limitation of usual activitiesSevereInability to carry out usual activities

#### 8.4 Known Adverse Event / Experience Prophylaxis Plan

## 8.4.1 Monitoring of Urine pH and Uric Acid Crystalluria

Acidic urine is a major, modifiable risk factor for uric acid urolithiasis, which form from uric acid crystals. Thus microscopic uric acid crystals in the urine (uric acid crystalluria; UAC) are an intuitive additional risk factor for these stones. Our experience in SURE-PD provides empiric evidence that identification of uric acid crystalluria by a central laboratory in the setting of low urine pH can in fact provide a useful further indication of increased risk of uric acid urolithiasis. Accordingly, urine samples will be collected at all on-treatment site visits for central laboratory urinalysis to determine pH and the presence of UAC, in a blinded manner. (See Schedule of Activities, Sec. 7.7.) Both risk factors will be

integrated into the following algorithm for triggering urine alkalinization therapy for uric acid stone prophylaxis.

# 8.4.2 Algorithm for Triggering Urine Alkalinization Method

Based on the premise that repeated measures of urinary risk factors for stone formation will be more reliable than a single measure, 194,195 persistently acidic urine (PAU) will trigger alkalinization treatment with potassium citrate (or an alternative means of urine alkalinization were potassium citrate [51] to be contraindicated) according to the schematized algorithm of Fig. 12. The threshold for alkalinization in response to PAU is lowered by greater urine acidity (i.e., the lowest pH values), by greater persistence of lower values, and by the presence of UAC.

#### Alkalinization Triggers

o PAU with lowest urine pH -Although the lowest urine pH value of ≤5.0 on the initial screening visit (SC1) is an enrollment exclusion criterion, it may occur at the baseline visit or as a finding in any subsequent

Figure 12. **Urine Alkalinization Flow Chart Triggers** > PAU with pH ≤5.0 (2 consecutive) > PAU with pH ≤5.5 (3 consecutive) > PAU with pH ≤5.5 (1 of last 2) if UAC low cit If cit newly low → pH ✓ in 2 wk < 6 6 - 7 full cit PAU = persistently acidic urine low cit = lower-dose potassium citrate\*\* UAC = uric acid crystals present = 10 mEq tid (<70 kg) or qid (≥ 70 kg) pH ✓ in 2 wk (using home urine sample shipped to central lab) and at next visit (when serum electrolytes, BUN, creatinine and CBC will also be checked as safety labs on cit). full cit = fuller-dose potassium citrate = 20 mEq tid (<70 kg) or qid (≥ 70 kg) stop = discontinue potassium citrate \* If pH <6 consecutively on **full cit** then reassess compliance and consult with Medical Monitor to consider increase up to 100 mEq/day potassium citrate in divided doses (tid or qid), or trial of an alternative alkalinizing agent such as sodium bicarbonate if cit not tolerated. \*\* Alternative, non-potassium alkalinizing agents such as sodium bicarbonate should be used in lieu of potassium citrate in those who have a history of peptic ulcer disease, are taking an anticholinergic agent (e.g., trihexyphenidyl), have another contraindication to potassium citrate, or do not tolerate it.

urine sample collected throughout the study. If it occurs in any two consecutive urine samples (first possible at the 3-week visit V01) it will trigger alkalinization per the algorithm outlined in Fig. 12.

o PAU with sustained lower urine pH – Three consecutive study urine pH values of ≤5.5 will trigger alkalinization (as in Fig. 12), unless the DSMB or SC determine that fewer (two) or more (four) consecutive study urine pH values of ≤5.5 will trigger alkalinization to better balance the benefits and risks of alkalinization in the trial.

o PAU with lower urine pH and UAC – If UAC is identified in the sediment of a urine sample, than a urine pH value of  $\leq 5.5$  either in the same sample or in the sample from the prior urine sample will trigger alkalinization (as in Fig. 12).

#### • Alkalinization Impact on Blinding

Subjects and site staff will be blinded to the specific urine pH and crystalluria test results to minimize unblinding to treatment assignment. Because urate-elevating inosine treatment does not have an appreciable effect on urine pH as demonstrated in SURE-PD, the rate of alkalinization due to low urine pH will be similar in placebo- and inosine-assigned subjects, also mitigating any unblinding effect. However, a difference in alkalinization rates may occur, because UAC is expected to occur primarily in inosine-treated subjects and would further lower the threshold for alkalinization (as above). Accordingly, if alkalinization is initiated in more inosine- than placeboassigned participants then the threshold for initiating alkalinization would be altered in placebo participants in order to maintain similar frequencies of alkalinization across treatments. For example, if the number of participants in the inosine group who have initiated alkalinization exceeds that in the placebo group by 2 or >2, then the placebo group alkalinization trigger for consecutive urine pH values <5.5 even in the absence of UAC would be 2 or 1, respectively (rather than 3 as in Fig. 12). Further, the DSMB will monitor rates of alkalinization, any alkalinization AEs and any urolithiasis AEs (in aggregate and by treatment assignment) and will periodically assess whether any change in the alkalinization protocol is warranted during the study.

#### • Alkalinization Protocol

Site staff will receive automated notification from the DCC of the need to initiate alkalinization within a few days of the urinalysis that triggers the protocol by the above criteria. The following steps should then be taken:

- Site staff will prescribe (via a central pharmacy) "lower-dose" potassium citrate, which depends on subject weight (as recorded most recently on a study visit):
  - Less than 70 kg: 10 mEq, in tablet form, po tid (with meals)
  - 70 kg or greater: 10 mEq, in tablet form, po qid (with meals and at bedtime)

The potassium citrate prescription may be written for a one month supply of tablets that will cover dosing at either the lower or higher dose -- for efficiency given the possibility that the subject may double the dose (from lower to higher) within two weeks of initiation. Accordingly, recommended prescriptions depending on subject weight are:

- [Less than 70 kg] 10 mEq tabs; # 180; sig: 1-2 po tid (with meals); refills: 5.
- [70 kg or greater] 10 mEq tabs; # 240; sig: 1-2 po qid (with meals and at bedtime); refills: 5.
- Staff will phone the subject to review the purpose, administration, potential adverse effects of potassium citrate, and plan rechecking urine pH in two weeks. In addition, staff will review recommendations for adequate hydration. The prescriber should review with the subject:
  - Any contraindications to potassium citrate, including a history of peptic ulcer disease, current use of an anticholinergic agent (e.g., trihexyphenidyl), hyperkalemia or renal insufficiency per most recent electrolyte measurements, or an active urinary tract infection.
    - o If potassium citrate were deemed contraindicated (or later found insufficient) then site staff may work with the Medical Safety Monitor to employ an

alternative dosing schedule or an alternative alkalinizing agent such as sodium bicarbonate.

- Potential adverse effects of potassium citrate, including minor gastrointestinal complaints, such as abdominal discomfort, vomiting, diarrhea, loose bowel movements or nausea, and rarely gastrointestinal bleeding. The subject should be instructed to check with site staff or another doctor at once if tarry stools or other evidence of gastrointestinal bleeding is noticed.
- The possibility of abnormal results of blood lab test that will be monitored regularly on subsequent visits, and if this is the first prescription of potassium citrate at either a 10 mEq or the 20 mEq dose then in 5-10 days at an unscheduled visit.
- The importance of taking each dose faithfully, 91 and without crushing, chewing or sucking the tablet, and to check with physician if there is trouble swallowing tablets or if the tablet seems to stick in the throat. Subjects should not change dosing alkalinization medication until instructed to do so based on follow-up urinalysis results.
- Instructions for obtaining and mailing to the central lab a urine sample 2 weeks following initiating the alkalinization mediation (using a kit and mailer to be received by courier mail).
- Site staff will receive automated notification from the DCC within a few days of any home (and visit) urine sample analysis for a subject on alkalinization therapy. The notification will include the assumptions of what the subject is currently taking for alkalinization therapy (e.g., low or higher dose potassium citriate or the equivalent) and recommendation to continue on this dosing, to reduce/discontinue it, or to increase it (according to algorithm outlined in Fig. 12).
  - Staff will phone the subject to review the results, confirm the assumptions of the subject's dosing when the urine sample was collected, and make the indicated recommendation to continue on this dosing, to reduce/discontinue it, or to increase it.
    - o For subjects on "lower-dose" potassium citrate who are instructed to increase it to "higher-dose" potassium citrate, they will be instructed to double their current dose. Depending on their weight:
      - less than 70 kg: 20 mEq, in tablet form, po tid (with meals)
      - 70 kg or greater: 20 mEq, in tablet form, po qid (with meals and at bedtime)
  - For any deviations from compliance with the medication site staff will contact the CCC who may engage the Medical Safety Monitor to obtain guidance.
  - Staff will review (as detailed above) the purpose, administration, potential adverse effects of potassium citrate, and plan for rechecking urine pH at home in two weeks if the subject is to increase or to reduce the alkalinization dose. Home recheck will not be performed if the subject is instructed to continue the current alkalinization dose or to discontinue it, or if the subject is scheduled for a site visit in the next two weeks.
- Subjects will be instructed to follow this algorithm for alkalinization for the duration of the treatment period of the trial. Any alkalinization therapy ongoing at the time of 24 month visit will be discontinued immediately after that visit (or at the time of study drug discontinuation if occurring earlier) irrespective of urine pH or sediment results at the visit.

## 8.4.3 Hyperkalemia and Other Laboratory Abnormalities

Current full prescribing information for potassium citrate indicates that laboratory tests should be checked every 4 months for:

- Electrolytes (to monitor for potassium elevation)
- Creatinine (to monitor for renal disease, a risk factor for hyperkalemic complications)
- CBC (to monitor for anemia as an indicator of gastrointestinal bleeding due to mucosal lesions, which have been observed rarely on solid potassium treatments at an estimated frequency of approximately 1 lesion per 100,000 patient-years).

Under the study protocol electrolytes and creatinine will be monitored even more frequently via routine laboratory testing no more than 3 months apart. A CBC will be added to the central lab tests in subjects treated with potassium citrate at any time since their last study visit.

## 8.4.3.1 Hyperkalemia

If hyperkalemia develops while a subject is taking potassium citrate, it should be suspended. Potassium testing should be repeated within 7 days of the suspension.

If serum potassium falls back into the normal range, then the potassium citrate will be resumed at a reduced dosage in an effort to find a lower dosage that does not produce hyperkalemia but on which urine pH remains at 5.5 or above.

If hyperkalemia remains, the potassium citrate will be discontinued. An alternative, non-potassium-based alkalinization measure may be tried if the Medical Safety Monitor and Site Investigator believe such a measure is warranted. If a non-potassium-based alkalinization measure is not warranted, then the subject should discontinue study drug.

If urine pH remains <5.5 on potassium citrate at the maximum tolerated dosage (i.e., not producing hyperkalemia, and up to 100 mEq/day), or on a non-potassium-based-alkalinization measure, then the subject will discontinue study drug due to 'unmitigated PAU.'

## 8.4.3.2 Rise in Serum Creatinine or Fall in Hematocrit or Hemoglobin

If a significant rise in serum creatinine or a significant fall in blood hematocrit or hemoglobin develops while a subject is taking potassium citrate, it should be suspended and the source of the abnormality determined.

If these abnormalities are attributable to irreversible renal disease or to gastrointestinal bleeding, then the potassium citrate should not be resumed. Consideration may be given to an alternative, non-potassium-based alkalinization measure if the Medical Safety Monitor and Site Investigator believe such a measure is warranted.

If urine alkalinization cannot be resumed or an alternative cannot be instituted, then a urine sample will be sent for central laboratory pH testing within 2 weeks. If urine pH is found to be <5.5 then the subject will discontinue study drug due to 'unmitigated PAU'.

## 8.5 Known Adverse Event / Experience Management Plan

#### 8.5.1 Urolithiasis

If urolithiasis occurs with symptoms of suggestive pain, hematuria or painless urolithiasis observed or if incidentally noted on imaging, the following steps should be undertaken:

- Seek prompt medical attention to diagnose and manage elimination of any stone(s)
- Medical evaluation and treatment (preferably at the time of symptom onset) should include assessment of
  - Serum urate measurement
  - o Urinalysis for pH; and initiation of alkalinization therapy as warranted
  - o Urine sediment examination for crystalluria (and type of any crystals)
  - o State of hydration assessment (by history and exam); and rehydration,  as warranted
- Submit stone, if available, for chemical analysis
- Study drug plan:
  - Suspend study drug until medical condition is stabilized (including resolution of symptoms that may be due to urolithiasis)
  - o Resume dosing if the analysis of the stone or associated sediment crystalluria indicates no uric acid or urate composition, or the subject is found not to have urolithiasis.
  - o If the analysis of the stone or associated sediment crystalluria indicates uric acid or urate composition, or is indeterminant, then:
    - Resume dosing if a remediable contributor (e.g., unduly elevated serum urate, low urine pH and/or dehydration) can be reasonably expected to be better controlled.
    - Discontinue study drug if there is no evidence of remediable source or precipitant of urolithiasis (e.g., no serum urate level above targeted range, no urine pH <6.0, no dehydration)
    - Discontinue study drug if there is evidence of remediable source or precipitant of urolithiasis but subject prefers not to continue on drug.

#### 8.5.2 Acute Gouty Arthritis

If gout-like acute arthritis develops, the following steps should be undertaken:

- Seek prompt medical attention to diagnose and treat
- Medical evaluation should include prompt serum urate level checks
- Study drug plan:
  - Suspend study drug during evaluation period
  - Resume drug if the diagnosis of gout is associated with a remediable above-range serum urate level that resolves within 4 weeks off study drug. Drug resumption must be accompanied by continuing close monitoring of serum urate.
  - o Discontinue study drug if the diagnosis of gout is confirmed without a remediable above-range serum urate level.

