#### 6.2 Other Assessments

# 6.2.1 Movement Disorders Society Unified PD Rating Scale (MDS-UPDRS)

The MDS-UPDRS will serve as the primary outcome variable of the study (as justified in detail in Sec. 3.2.3) and will be conducted at all standard visits beginning with the 2nd screening visit. The MDS-UPDRS was designed by movement disorders experts to address weaknesses of the original UPDRS (e.g., by adding questions on constipation and sialorrhea) while preserving its overall format. The MDS-UPDRS has four parts:

- Part I (non-motor experiences of daily living), comprising
  - o Part IA concerning behaviors that are assessed by the Site Investigator with all pertinent information from patients and caregivers
  - o Part IB that is completed by the patient with or without the aid of the caregiver, but independently of the Site Investigator.
- Part II (motor experiences of daily living), designed to be a self-administered questionnaire like Part IB, but similarly can be reviewed by the Site Investigator to ensure completeness and clarity.
- Part III (motor examination) has instructions for the rater to give or demonstrate to the patient; it is completed by the clinician rater.

• Part IV (motor complications) with instructions for the rater and also instructions to be read to the patient. This part integrates patient-derived information with the rater's clinical observations and judgments and is completed by the rater.

Subjects will self-administer Parts IB and II, but will review responses for accuracy and clarity with the Site Investigator or Coordinator. Parts IA, III and IV must be conducted by the Site Investigator. Parts I, II, and III will be conducted at study visits as indicated on the Schedule of Activities (Sec. 7.7). Part IV will be conducted at visits where MDS-UPDRS Parts I-III are conducted/collected but only on subjects who have started on symptomatic therapy after the Baseline visit. Use of MDS-UPDRS is responsive to core instrument recommendations for the Quality of Life subdomain of the NINDS CDEs for PD, and to FDA guidance encouraging use of patient-reported outcomes (PROs) as a substantial portion of the responses are patient-reported. The same Site Investigator should assess all subjects on parts IA and III of the MDS-UPDRS at all study visits.

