## 7.2.2 Post Study Visit Telephone Calls

Beginning with the Baseline Visit, serum urate test results will not be provided to sites. Instead the serum urate result will only be provided to an unblinded DCC Programmer and used in an algorithm to determine if a subject's study drug should be increased, decreased, or remain steady. (See Sec. 5.1.2.3)

If serum urate level warrants altering capsule dosing, the DCC will notify both the Site Investigator and Coordinator by email within 3 days of the visit. The Site Investigator or Coordinator should immediately notify the subject and update the Dose Management Log. Dosage increases, reductions, or holds should be initiated as soon as the subject is notified.

If the most recent urine pH/sediment results trigger the initiation or change of alkalinization therapy, then the Site Investigator or Coordinator should immediately notify the subject on how to begin or modify use of potassium citrate (or an alternative alkalinizing agent) according to the alkalinization algorithm in Sec. 8.4.2.

A follow-up phone call will take place after each study visit once the site is informed of a dosage change. The following will be performed and documented during the call:

• Inform the subject to either increase, reduce or hold their study drug

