## 7.5 On-Study/Non-Standard Evaluations

## 7.5.1 Unscheduled Visit (Visit U01, U02, etc.)

An unscheduled visit may be performed at any time during the study at the subject's request or as deemed necessary by the Site Investigator. The date and reason for the unscheduled visit should be recorded in the source documentation.

In most cases, an unscheduled visit will be warranted due to an AE, significantly abnormal lab values, permanent discontinuation of study drug before 24 month visit, initiation of treatment with a thiazide 1-4 weeks earlier, or need for an in-person assessment for possible initiation of dopaminergic therapy.

The following procedures and evaluations at a minimum are to be performed at an Unscheduled Visit:

- Review and document concomitant medications
- Assess and document AEs
- Assess need for dopaminergic therapy (if need has not been determined at a previous visit)
- Obtain serum urate for blinded central analysis if subject initiated thiazide treatment 1-4 weeks earlier, or if otherwise warranted based on the Site Investigator's judgment
- Update the Dose Management Log as needed

If the reason for the unscheduled visit is that the participant is permanently discontinuing drug at the visit, whether by choice, or for reasons concerning the health or well being of the subject, the following additional procedures and evaluations should be completed:

• Assess blindedness to treatment assignment (Investigator, Coordinator and subject)

- Retrieve all previously dispensed study drug and calculate compliance (Note: If study drug has not already been discontinued and there is no medical reason to warrant otherwise, the final dose will be taken when the last dose of the day is normally taken on the day prior to the visit. No study drug is to be taken during or after the study visit.)
- Record last dosing on Dose Management Log
- If participant consented to the optional future biomarker study a blood sample will be taken (please see section 6.2.14 for information about altered sample collection schedule)

In addition as warranted by the purpose of the unscheduled visit, the following procedures and evaluations may be performed at the discretion of the Site Investigator:

- Obtain weight and orthostatic vital signs (blood pressure, heart rate)
- Obtain blood and/or urine for additional study chemistry or hematology tests, or other laboratory testing if warranted based on the Site Investigator's judgment

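### The rules for resuming or stopping study drug after gout, or after a uric acid or indeterminate stone, turn on serum urate values withheld from sites, and Section 8.5 is not tied to the existing blinded route.

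*Protocol*

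**What the plan says.** **The decision rules.** Protocol 8.5.2 (gout) has two branches. One is "Resume drug if the diagnosis of gout is associated with a remediable above-range serum urate level that resolves within 4 weeks off study drug"; the other is "Discontinue study drug if the diagnosis of gout is confirmed without a remediable above-range serum urate level". It also says "Medical evaluation should include prompt serum urate level checks" and asks for close urate monitoring once drug is resumed. Protocol 8.5.1 (stones) lists urate, urine pH and sediment in the work-up of every stone. If the stone or the associated crystals show uric acid or urate, or the result is indeterminate, continuation depends on whether there was a remediable contributor. The examples given for finding none are "e.g., no serum urate level above targeted range, no urine pH <6.0, no dehydration".

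**The blind.** Protocol 7.2.2: "Beginning with the Baseline Visit, serum urate test results will not be provided to sites". The result goes to an unblinded DCC programmer, and sites receive only a dosing instruction. Protocol 8.4.2: "Subjects and site staff will be blinded to the specific urine pH and crystalluria test results". SAP 2.7 lists the medical monitor among those blinded, and Protocol 11.2.1 bars the unblinded staff from passing on treatment-specific results. Protocol 3.2.4.2 and 8.8 expect stones and most emergencies to be handled without revealing assignment.

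**The rater.** Protocol 6.2.1: "Parts IA, III and IV must be conducted by the Site Investigator". Under 6.2.5 the same investigator judges need for dopaminergic therapy, and scores after it is started are censored from the primary analysis (10.5.1).

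**The route that exists.** For unscheduled visits, Protocol 7.5.1 has the line "Obtain serum urate for blinded central analysis", which applies after a thiazide is started or when the investigator otherwise judges it warranted. Section 8.5 does not refer to it.

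**The concern.** Section 8.5 asks for a decision based on values that other sections withhold from the site, and it does not say who reads them or who applies the rule. If the site obtains the urate itself, the blind is broken for that participant. If it keeps to the blind, it cannot tell which branch applies.

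The events that trigger the rule are expected mainly on inosine. Any unblinding would therefore differ by arm, and it would reach the person who scores part of the primary outcome and whose judgement on dopaminergic therapy determines when that outcome is censored.

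**Working it through.** The plan gives no figure for this point, so the check is a comparison of sections followed by a rough sizing.

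**1. What each decision needs, and who may see it**

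| Element | Used in | Visible to site? |
|---|---|---|
| Urate above target range | 8.5.1, 8.5.2 | No (7.2.2) |
| Urate resolving within 4 weeks off drug | 8.5.2 | No (7.2.2) |
| Urate monitoring after resumption | 8.5.2 | No (7.2.2) |
| Urine pH, crystals | 8.5.1 | No (8.4.2) |
| Hydration, stone analysis | 8.5.1 | Yes |

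The gout rule rests on urate alone. The stone rule can also be met through pH or hydration.

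**2. Which value reveals the arm**

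Entry requires urate of 5.7 mg/dL or lower at the first screening visit (4.1), and sites review the screening values with the participant (7.1.2, 7.1.4). In phase 2 every placebo participant kept a mean below 6.0 mg/dL (2.2.3). The expected baseline mean is 4.5 mg/dL (10.3.1) and the mean target on inosine is 7.5 mg/dL (2.1.1). The upper limit of the target range is 8.0 mg/dL.

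As an illustration, take urate as normal with mean 4.5 on placebo and 7.5 on inosine. The documents give no within-arm SD, so 0.5 to 1.3 mg/dL is assumed; 1.3 is the population SD quoted in 2.1.1.

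P(urate > 8.0) = 1 − Φ((8.0 − mean)/SD)

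| SD | Placebo | Inosine |
|---|---|---|
| 0.5 | about 0 | 0.16 |
| 0.8 | 0.000006 | 0.27 |
| 1.3 | 0.0035 | 0.35 |

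At the widest SD the ratio is 0.3503/0.00355 ≈ 99. These are probabilities for a routine value, not for urate at the time of an attack, so they show direction and order of magnitude only. It follows that the gout resume branch is, in practice, open only to inosine participants. Urine pH is different: 8.4.2 states that inosine has no appreciable effect on it.

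**3. How many participants**

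Inosine arm: 270/2 = 135. Maximum exposure: 135 × 2 = 270 person-years.

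- Stones at the phase 2 moderate-arm rate of 7% (2.2.3): 135 × 0.07 = 9.45, about 9 to 10.
- Stones reaching the urate-dependent rule: of the three phase 2 stones, one was documented as uric acid, one was calcium-based and one was not analysed. If 1/3 to 2/3 qualify (an assumption from three stones), 9.45/3 = 3.2 to 9.45 × 2/3 = 6.3.
- Excess gout at 0.3 to 2.6 per 100 person-years (2.2.2): 270 × 0.003 = 0.8 to 270 × 0.026 = 7.0.

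**The case against.** **A blinded route does exist.** A reader might infer that the protocol offers none. Section 7.5.1 names an adverse event among the usual reasons for an unscheduled visit and allows blinded central urate when the investigator thinks it warranted. Section 5.1.2.3 applies DCC titration to unscheduled on-treatment values as well. This stands, and it narrows the point: Section 8.5 is not linked to that route, and nothing says the route feeds the resume-or-stop decision.

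**Urine pH does not unblind.** A reader might take a sighting of pH below 6.0 as revealing treatment. It would breach the planned blind to pH, but given the statement in 8.4.2 it would not identify the arm.

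**The numbers could be pushed much higher.** Applying the 3.8% to 25% stone rates from the multiple sclerosis trials gives 135 × 0.038 = 5.1 to 135 × 0.25 = 33.8. Adding gout gives roughly 6 to 40 participants. The documents do not support that range. The 25% is 4 of 16 participants with urate above that study's target and before standard prevention, and none of those trials managed urine pH. The total also counts stones that resume drug whatever the urate, and it sums extremes.

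**The event is itself a clue, and much of the data is untouched.** SAP 6.8.7 lists earlier stones and gout among the predictors of treatment belief. Phase 2 stones came after more than 4 months on drug, and scores after dopaminergic therapy, expected in 70%, are censored. These facts limit the size. They do not remove the conflict, because a urate value is far stronger evidence than the event, and the questionnaire can detect unblinding but not prevent it.

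**Relaying a bare decision is not enough.** After gout, a plain instruction to resume would itself point to inosine. Hydration, and whether a contributor can be controlled, need the site's judgement. Both objections stand and shape the fix.

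**Conclusion.** The conflict is real and should be resolved. As written, a blinded site cannot apply the study-drug rules in 8.5.1 (uric acid or indeterminate stones) and 8.5.2 (gout) without on-treatment values that 7.2.2 and 8.4.2 withhold. Serum urate is the value that reveals the arm.

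The size is limited and uncertain. Per 135 inosine participants, expect about 9 to 10 stones, perhaps 3 to 6 of them reaching the urate-dependent rule, and about 1 to 7 excess gout episodes. The stone figures rest on very few phase 2 events. The gout figures assume two full years for everyone, although SAP 4.6 records early closeout, and phase 2 had no gout at all. In the other direction, SAP 2.6 reports more stones than expected, without giving a rate. The work-up in 8.5.1 lists urate for every stone, so exposure to the value could extend beyond the participants whose decision depends on it.

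A reader might go further and conclude that the primary result would be materially biased. The documents do not allow that bias to be sized. They support only that unblinding would fall mainly on inosine and has a path to both scores and censoring.

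**What to change.** Reconcile 8.5.1 and 8.5.2 with 7.2.2, 7.5.1 and 8.4.2, leaving every clinical criterion and all acute care as they are:

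1. State that study samples for urate, urine pH and crystals used in these decisions, and urate for monitoring after resumption, go to blinded central analysis by the route in 7.5.1.
2. State that the site supplies what it has to judge: hydration, stone analysis, and whether a contributor can be controlled.
3. State that the unblinded DCC applies the existing urate and pH conditions and returns only an instruction, as it does for titration (7.2.2) and alkalinization (8.4.2).
4. For placebo participants, evaluate the urate condition on the hypothetical urate in 5.1.2.3: observed urate + (U + v + w) × number of placebo capsules. With 0 capsules during suspension the added term is 0, so the hypothetical value falls back to the observed one off drug, as it would on inosine. An instruction to resume then no longer identifies the arm.

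The cost is protocol wording and one further automated DCC message; the central laboratory and unblinded staff are in place. The downside is a delay of a few days while study drug is already suspended. Unblinding through tests ordered by outside clinicians, or through the event itself, remains.
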